## 7 DATA CONVENTION

All data analysis will be performed by Trial Runners, LLC after the study is completed and database has been locked and released for unmasking. Statistical programming and analyses will be performed using SAS® Version 9.4 or higher. Output will be provided in RTF format for tables and PDF format for tables, listings, and figures using landscape orientation. All study data will be listed by subject, treatment, and visit (as applicable), based on all enrolled subjects.

### 7.1 Missing Data

Efficacy data related to eye anatomy or visual function that is collected after rescue treatment (i.e., treatment for DME or PDR other than study medication) will be treated as missing data. Unless, otherwise stated, missing data will be handled using the following approach:

- For start date, partial dates will have first day of the month imputed if day is missing, and January of that year will be imputed if month is missing. If both day and month are missing, January 01 will be imputed.
- For end date, partial dates will have last day of the month imputed if day is missing, and December of that year will be imputed if month is missing. If both day and month are missing, December 31 will be imputed.
- Missing data are imputed using Last Observation Carried Forward (LOCF) for all visits except screening/baseline; screening/baseline values are not carried forward.
- For vision related efficacy measurements (Tables 14.2.1.x, 14.2.2.x, 14.2.3.x, 14.2.4.x, 14.2.5.x, 14.2.6.x, 14.2.7.x, 14.2.8.x, 14.2.10.x, 24.2.11.x, 14.2.12.x, 14.2.13, 14.3.12.3, 14.3.13.3, 14.3.14.2x, 14.3.14.5) subjects receiving rescue treatment will be handled differently to reflect their status as a treatment failure and to avoid confounding of the effects of rescue treatment with the effects of study drug. Specifically, last pre-rescue data are carried forward for LOCF analysis. If rescue and DRSS occur on the same day, DRSS from that day is carried forward. For Observed Case (OC) analyses, results post-rescue are omitted, and last pre-rescue data are carried forward. Note that for DRSS scales involving both eyes (Person and Binocular scale) the carry forward rules apply only to the rescued eye in calculation of the combined score.
- Where severity or relationship is missing for adverse events, most conservative imputation will be made.

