In pivotal trials of intravitreal anti-VEGF (vascular endothelial growth factor) effects on diabetic macular edema (DME), it was observed that treatment also had beneficial effects on DR. After 1 year of treatment with Eylea®, 33.5% of subjects treated monthly and 28.4% of subjects treated bi-monthly improved by ≥ 2 steps on the ETDRS severity scale, compared to 10.9% in the laser treatment group (Korobelnik et al., 2014). Similarly, in the RISE and RIDE trials with Lucentis®, 46.9% of subjects treated with 0.3 mg monthly and 46.8% of subjects treated with 0.5 mg monthly for 2 years had a ≥ 2 step improvement in DR, compared to 6.8% of subjects treated with sham injections (Ip et al., 2012). There was also a decrease in the percent of subjects who worsened by ≥ 2 steps after 2 years of treatment (2.5%, 2.0%, and 12.4% in the 0.3 mg Lucentis, 0.5 mg Lucentis, and sham groups, respectively). On the basis of these data, Lucentis and Eylea have been approved for the treatment of DR in patients with DME. However, the efficacy of anti-VEGF therapy for the treatment of DR in patients without center-involved DME is unproven. Two trials have recently been initiated to test the efficacy of Eylea in this population (the PANORAMA study - NCT02718326 sponsored by Regeneron; and Protocol W - NCT02634333 sponsored by DRCR.net). However, it is important to note that eyes with non-proliferative diabetic retinopathy (NPDR) and no DME have little visual dysfunction and thus the burden of multiple binocular intravitreal anti-VEGF injections may be unacceptable in this population. The objective of the present study is to examine the efficacy of AKB-9778 subcutaneous administration in the treatment of NPDR in patients without DME.

AKB-9778 is a first-in-class molecule in development for the treatment of diabetic eye disease, including DME and DR. AKB-9778 is a small molecule Tie2 (tyrosine kinase with immunoglobulin-like and EGF-like domains 2) activator that works through inhibition of VE-PTP (vascular endothelial-protein tyrosine phosphatase), otherwise known as HPTP β (human protein tyrosine phosphatase β), enhancing Tie2 activation and signaling. Tie2 is a receptor

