7.3 Ocular Eligibility Criteria

For a subject to be included in the study, at least one eye must meet all ocular inclusion and exclusion criteria. If both eyes meet all ocular eligibility criteria, then the eye with the worse ETDRS DRSS should be designated the study eye, and the other eye designated as a qualified fellow eye; in this case, the Central Image Reading Center will confirm selection of the study eye.

7.3.1 Study Eye / Qualified Fellow Eye Inclusion Criteria:

- 1. Moderate to severe NPDR (ETDRS Level 43 – 53 inclusive) as confirmed by the Central Image Reading Center
- 2. No evidence of center involved DME on SD-OCT as confirmed by the Central Image Reading Center
- 3. No history of treatment for DME or DR within 12 months prior to Day 1 and no history of treatment with Iluvien® within 36 months prior to Day 1
- 4. ETDRS BCVA letter score ≥ 70 (Snellen 20/40 or better)

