### 7.2 Descriptive Statistics

For continuous variables, descriptive statistics will include the number of subjects (n), mean, standard deviation (SD), median, minimum and maximum. Categorical variables will be summarized using absolute and relative frequencies (i.e., counts and percentages). For categorical analyses, eyes that receive rescue therapy will be considered as treatment failures. Safety and PK data will be analyzed as collected.

All efficacy data will be summarized by treatment groups and overall using appropriate descriptive statistics. Summaries will be presented for both the MITT and PP populations, where applicable. Due to the small number of subjects enrolled at each center, all summaries and analyses will be performed using data pooled across centers. Unscheduled data, such as information from unscheduled visits or investigator comments, will be included in the data listings. In general, these data will be excluded from the summary tables unless otherwise specified.

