### **8.3 Protocol Deviations**

The number and percentage of subjects with major protocol deviations will be summarized by treatment groups and for all subjects for the safety population. The protocol deviations that will be summarized include: informed consent, inclusion/exclusion and randomization, study drug administration and assignment at site, improper protocol procedures at site (missed, repeated, not per protocol), site's failure to report SAE/AE, visit out of window (missed, early, late), subject's non-compliance with subcutaneous study drug (<70% of expected doses administered), subject's use of prohibited concomitant medication, subject's failure to follow instructions and other. A subject listing will be provided that includes the date of the deviation, the deviation description and the classification of whether the deviation was judged to be major or minor.

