## **10.1 Primary Efficacy Endpoint Analysis**

The primary hypotheses to be tested is that AKB-9778 15 mg twice daily and AKB-9778 15 mg once daily will be superior to placebo in the improvement of DR as measured by the ETDRS severity scale change from baseline at 48 weeks. Specifically, the primary endpoint is the percentage of subjects with an improvement in study eye severity of DR (ETDRS DRSS) of  $\geq 2$  steps at 48 weeks without need for treatment of PDR or DME (by IVT, laser, or vitrectomy) in the study eye. DRSS scores used for all analyses will be obtained from final adjudicated grading by the central reading center (Fundus Photograph Reading Center for the standard field images).

The primary hypotheses will be tested in the MITT population using a Fisher's Exact Test with a 2-sided 5% significance level. AKB-9778 15 mg twice daily will be tested first. If this is found to be statistically significant, then AKB-9778 15 mg once daily will be tested for statistical significance, at the same significance level. Cochran-Mantel-Haenszel (CMH) test stratified for baseline ETDRS DRSS (levels 4, 5 and 6) will also be used for testing primary hypothesis in the MITT population. Missing data will be imputed using LOCF; baseline values will not be carried forward.

As a sensitivity analysis, primary hypothesis will be tested using Fisher's Exact test, and CMH test stratified for baseline ETDRS DRSS (levels 4, 5 and 6) on OC in the PP population.

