# Note to File

**Clinical Study Protocol AKB-9778-CI-5001: PHASE 2 DOUBLE-MASKED, PLACEBO-CONTROLLED STUDY TO ASSESS THE SAFETY AND EFFICACY OF SUBCUTANEOUSLY ADMINISTERED AKB 9778 15MG ONCE DAILY OR 15MG TWICE DAILY FOR 12 MONTHS IN PATIENTS WITH MODERATE TO SEVERE NON-PROLIFERATIVE DIABETIC RETINOPATHY**

To: Statistical Analysis Plan, Final Version 27Feb2019

Date: 03-Mar-2019

Re: Criteria used to define Progression to Vision-Threatening Complications (DME and/or PDR)

---

Criteria used to define Progression to Vision-Threatening Complications (DME and/or PDR):

Qualified eyes were included as progressors if one or more of the following conditions occurred during the trial:

1. An AE of DME was entered that was either treated or was confirmed by the reading center as having either center involved retinal cyst, center involved retinal edema, center involved subretinal fluid, or central subfield thickness >300 microns.
2. An AE of PDR, NVE, NVD, or vitreous hemorrhage
3. IVT with anti-VEGF therapy or corticosteroid with indication for treatment documented as either DME or PDR
4. PRP, Grid laser, or focal laser with indication for treatment documented as either DME or PDR
5. An increase in central subfield thickness of  $\geq 20\%$  at last observation
6. DRSS score of  $>53$ , indicating PDR, at last observation

AERPIO SIGNATURE

DATE

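### Rescue is defined only as treatment for DME or PDR, so a study eye treated for NPDR, or injected with anti-VEGF for another reason, keeps its later DRSS and can count as a responder

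*SAP*

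**What the plan says.** **SAP 7.1** treats eye-related efficacy data as missing when "collected after rescue treatment (i.e., treatment for DME or PDR other than study medication) will be treated as missing data". For the listed vision-related tables it carries the last pre-rescue value forward. It gives two reasons: rescued subjects are treatment failures, and the effect of rescue should not be mixed with the effect of study drug.

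**SAP 7.2** adds the responder rule: "For categorical analyses, eyes that receive rescue therapy will be considered as treatment failures". It relies on the definition in 7.1.

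**SAP 10.1** (and Protocol 11.7 in the same terms) requires the 2-step improvement to occur "without need for treatment of PDR or DME (by IVT, laser, or vitrectomy) in the study eye". Routes are named, but only for those two indications.

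**Protocol 7.3** uses a wider term at entry: "No history of treatment for DME or DR within 12 months prior to Day 1".

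**Protocol 8.4.3 and Appendix B** set conditions for treating PDR or DME on study. They do not mention the same agents given for NPDR or for another eye condition.

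**SAP 8.3** lists "subject's use of prohibited concomitant medication" as a class of deviation, but the supplied text has no list that names ocular agents.

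**The concern.** Treatment with an agent that itself moves DRSS confounds the comparison, whatever indication the site records. Protocol section 4 cites 2-step improvement in 28.4% and 33.5% of aflibercept subjects at 1 year, against 10.9% with laser, in DME populations.

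The clearest gap is treatment of the study disease itself. Anti-VEGF given for NPDR within the year before Day 1 makes an eye ineligible. The same injection at Month 6 triggers neither the failure rule nor the carry-forward rule. The protocol says that in eyes without center-involved DME "the efficacy of anti-VEGF therapy for the treatment of DR in patients without center-involved DME is unproven", and notes that two trials had begun to test it there, so such use is conceivable during this study.

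A second, smaller gap is intravitreal anti-VEGF for an unrelated condition that arises after entry.

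The primary MITT response rate is at stake, and with it the BID test, which must be significant before QD can be tested.

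**Working it through.** **Step 1. How an eye would be classified.** Take a study eye at level 47 that receives intravitreal anti-VEGF at Month 6 for NPDR, with no PDR or DME.

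| Rule | Trigger | Applies? |
|---|---|---|
| SAP 7.1 missing / carry-forward | treatment for DME or PDR | No |
| SAP 7.2 treatment failure | rescue as defined in 7.1 | No |
| SAP 10.1 / Protocol 11.7 endpoint clause | treatment of PDR or DME by IVT, laser or vitrectomy | No |
| Protocol 7.3 entry criterion | treatment for DME or DR | Yes, but only before Day 1 |

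The eye keeps its observed Week 48 DRSS and is a responder if that has improved by 2 or more steps.

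**Step 2. The plan's own figure.** Inputs from SAP 3.1: 45 evaluable per arm, 30% against 5%, Fisher's exact test, two-sided 0.05. Power is the sum, over all outcome pairs with p ≤ 0.05, of the product of the two binomial probabilities. This gives 86.3%, which reproduces the stated figure of over 85%. Also 45 / (1 − 0.10) = 50 per arm. At 50 per arm the same calculation gives 89.9%.

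**Step 3. Illustration for one placebo eye.** The documents give no rate of such treatment, so one eye in 50 is an assumption. Let r be its chance of a 2-step gain, taken from the 1-year figures in Protocol section 4.

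Placebo rate = (49 × 0.05 + r) / 50

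- r = 0.284: (2.45 + 0.284) / 50 = 5.47%; power at 50 per arm is 88.0%
- r = 0.335: (2.45 + 0.335) / 50 = 5.57%; power at 50 per arm is 87.6%

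The expected excess is 0.284 − 0.05 = 0.23 to 0.335 − 0.05 = 0.29 of one responder. At 45 per arm, a placebo rate of 5.5% gives 83.8%, against the planned 86.3%.

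**Step 4. The same eye counted as a non-responder.** The placebo rate becomes 49 × 0.05 / 50 = 4.9%, and power at 45 per arm is 86.8%. The wider definition costs no power in this scenario.

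**Step 5. The opposite direction.** Suppose such eyes occur only in an active arm whose true rate is 5%, with 50 per arm. The chance of a significant result favoring drug is 0.36% with none. It is 0.55% if 2% of eyes are treated and respond at 30%, and 2.0% if 6% are treated and respond at 46%. All are below 2.5%.

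**Step 6. Sensitivity to a single eye.** In a close result one eye can decide: 10/50 against 2/50 gives p = 0.028, and 10/50 against 3/50 gives p = 0.071. At the planned active rate it cannot: 15/50 against 3/50 gives p = 0.003, and against 4/50 gives p = 0.009.

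**The case against.** The strongest case against is that such eyes will be rare and the plan already limits them.

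- **Exclusions.** Protocol 7.3.2 excludes other sight-reducing ocular disease, past non-infectious uveitis, recent ocular surgery and any condition that may need intervention.
- **Appendix B.** It restricts even PDR treatment so that monotherapy can be judged, so treating NPDR alone would go against its purpose. Protocol section 4 also doubts that repeated injections are acceptable in this population.
- **Per-protocol re-test.** It can drop subjects whose deviation affects DRSS.

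This stands as to size. It does not close the gap: entry criteria do not prevent later treatment, Appendix B does not address NPDR, and the primary analysis is MITT.

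A reader might infer more than the documents support, in four ways.

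- **That the Note to File also defines rescue.** Its lines "IVT with anti-VEGF therapy or corticosteroid with indication for treatment documented as either DME or PDR" and "PRP, Grid laser, or focal laser with indication for treatment documented as either DME or PDR" define progression to DME or PDR. Indication belongs there.
- **That power could fall much further.** Power at 50 per arm is 85.7% at 6% placebo response and 80.9% at 7%. A 7% rate needs about three treated placebo eyes responding near 47%, which is a 2-year result of monthly dosing in DME.
- **That the rule favors drug.** The direction depends on the arm, and no passage shows which arm would receive more such treatment.
- **That any laser, vitrectomy or steroid is an equal threat.** The only laser figure is the 10.9% control arm, and there is no DRSS figure for steroid or vitrectomy. Failing an eye for repair of an unrelated retinal tear is a debatable choice of estimand.

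**Conclusion.** The gap is real on the text. The rescue definition is narrower than the entry criterion and narrower than the SAP's own reason for having it, and no supplied passage closes it for the MITT analysis. The likely effect is small: about 2 percentage points of power for one placebo eye in 50, assuming a response at the 1-year anti-VEGF rates from DME trials. An incidental injection may well do less than those regular regimens. If the eye is in an active arm the bias runs the other way. The design figures are unaffected. The point merits correction because it is cheap and removes dependence on how a site words an indication; it does not put the trial's conclusion in doubt.

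**What to change.** Before unmasking, amend SAP 7.1 and 10.1 so that, for analysis, rescue of the study eye means either of these:

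1. any treatment of DR, DME or PDR by intravitreal injection, laser or vitrectomy;
2. any intravitreal anti-VEGF or corticosteroid, whatever the recorded indication.

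From that date the eye is a non-responder for categorical endpoints, and its last pre-treatment value is carried forward for continuous ones. Apply the same rule to a qualified fellow eye in its own endpoints. Record the difference from Protocol 11.7 in SAP 1.1, which now reports no change from the protocol.

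Put laser, vitrectomy or periocular steroid for clearly unrelated disease into a sensitivity analysis that counts those eyes as non-responders. Leave the Note to File criteria as they are.

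**Cost:** SAP wording and one derivation. Protocol 9.2.1 already requires all medications and treatments to be recorded through Month 12, and SAP 9.2 already splits ocular medications by study, qualified fellow and unqualified fellow eye. Confirm that laser and vitrectomy for other reasons are also captured by eye. The downside is that an occasional eye injected for an unrelated disease counts as a non-responder. Only the analysis changes; clinical management does not.

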### **9.2 Prior and Concomitant Medications**

Prior and concomitant medications will be presented for each subject coded per the World Health Organization (WHO) Anatomical Therapeutics Chemical (ATC) Drug dictionary. Prior medication are those medications that were started anytime and were stopped within 30 days prior to visit 1. Concomitant medications are those medications that were started anytime after visit 1 and before the last study visit or started anytime before visit 1 and were ongoing on or after visit 1. The data will be summarized by ATC dictionary (WHO DDE B2 September 1, 2017) drug class and generic name and classified as non-ocular and ocular prior and concomitant medications. Further, ocular prior and concomitant medications are presented for study eyes, qualified fellow eyes and unqualified fellow eyes. Descending sorting order by the frequency of ATC drug classification, and within that descending order by the frequency of generic name will be followed. A separate listing for both non-ocular and ocular prior and concomitant medication will present be presented.

Medications with partial dates that do not allow determination of whether prior or concomitant will be considered concomitant. Prior and concomitant medications are presented for safety population.

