## **11.1 Safety Endpoint Analysis**

### **11.1.1 Adverse Events**

All AEs reported during the study and follow-up period will be recorded and coded using MedDRA version 20.1 terminology. An AE will be considered as treatment-emergent if it has an onset during the treatment period or is pre-existing and worsens after the first dose of study medication is administered. When the date of AE is same as date of randomization, the site will be queried to ensure timing of AE start relative to first dose is determined.

The incidence of all reported treatment-emergent adverse events (TEAEs) will be summarized using system organ class and preferred term by treatment group and overall, using counts and percentages. All adverse events will also be presented by relationship and severity. Further, serious adverse events and adverse events leading to discontinuation will also be presented.

Separate analyses will be performed for ocular and non-ocular TEAEs. For ocular TEAEs, the subject will be considered to have had the TEAE if at least one eye had the TEAE. Ocular TEAEs will be summarized separately for all eyes, study eyes, all qualified eyes (study eyes and qualified fellow eyes) and unqualified fellow eyes.

Subjects may have more than one AE per system organ class and preferred term. At each level of subject summarization, a subject will be counted once if they reported 1 or more events and will be reported with the highest severity. In cases where severity or relationship is missing, the most conservative approach will be taken (i.e. highest severity and assumed to be related).

A listing of TEAEs will be generated showing adverse event location (OD, OS or non-ocular), duration of TEAEs with onset date, severity, relationship with study medication and change in status of ongoing event. Also, listing for serious adverse events, and adverse events leading to discontinuation will be generated.

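### SAP 7.1 has no first-dose floor for partial AE start dates, so some on-treatment AEs from the month (or year) of first dose are dated before Day 1 and lost from the TEAE tables

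*SAP*

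**What the plan says.** SAP 7.1 sets a default for all data: "Unless, otherwise stated, missing data will be handled using the following approach". For start dates the rule is "For start date, partial dates will have first day of the month imputed if day is missing". A missing month becomes January, and "If both day and month are missing, January 01 will be imputed". First dose is not mentioned.

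SAP 11.1.1 (and protocol 11.6 in the same terms) defines a TEAE by its onset date: "An AE will be considered as treatment-emergent if it has an onset during the treatment period or is pre-existing and worsens" after the first dose. SAP 7.3 makes the day of first dose Day 1. Protocol 10.3.1 collects AEs from informed consent, and screening can last 28 days, so the database holds pre-dose events that only the onset date separates from TEAEs.

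Three nearby rules handle uncertainty, but none covers a partial AE onset date:

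- SAP 11.1.1 has a timing check: "When the date of AE is same as date of randomization, the site will be queried". It is triggered by equality with the randomization date.
- The same section says "In cases where severity or relationship is missing, the most conservative approach will be taken". This covers severity and relationship, not onset.
- SAP 9.2 says "Medications with partial dates that do not allow determination of whether prior or concomitant will be considered concomitant". This covers medications only.

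**The concern.** An earliest-possible-day rule is harmless for an event that is clearly before or clearly after first dose. It matters when the known part of the date covers both sides of first dose. The rule then always chooses the pre-dose side, so a new on-treatment event no longer counts as having its onset during treatment. The worsening limb of the definition recovers it only if it later worsened.

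The SAP takes the cautious side for ambiguous medications and for missing AE severity or relationship, but not for TEAE status. Safety and tolerability is a secondary objective, and SAP 11.1.1 builds its main incidence tables on TEAEs. With 50 subjects planned per arm, one subject lost from a row moves its incidence by 1/50 = 2 percentage points.

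**Working it through.** The plan states no figure on this point, so there is none to reproduce. The check applies the SAP 7.1 rule to every possible date.

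**Inputs.** Treatment lasts 336 days (protocol 9). Day 1 is the first-dose date (SAP 7.3). Assumptions, not from the documents: first dose is uniform over a 365-day year, and onset is uniform over the treatment days. That gives 365 × 336 = 122,640 pairs of first-dose date and onset date.

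**Day missing.** The imputed date is the 1st of the onset month. It precedes first dose only if onset is in the same calendar month as first dose and first dose was not on the 1st. In a month of L days, first dose on day d leaves L − d + 1 on-treatment days in that month. Summing over d = 2 to L gives L(L − 1)/2 affected pairs.

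- Seven 31-day months: 7 × 465 = 3,255
- Four 30-day months: 4 × 435 = 1,740
- One 28-day month: 378
- Total 5,373; share 5,373 / 122,640 = 4.4%

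By first-dose date the share runs from 0% (dosing on the 1st) to 30/336 = 8.9% (dosing on the 2nd of a 31-day month). Within the first-dose month itself, 93.6% of on-treatment days are affected.

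**Day and month missing.** The imputed date is 1 January of the onset year. It precedes first dose if onset is in the same calendar year and first dose was not on 1 January. With first dose i days after 1 January, min(336, 365 − i) treatment days fall in that year.

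- i = 1 to 29: 29 × 336 = 9,744
- i = 30 to 364: 335 + 334 + … + 1 = 56,280
- Total 66,024; share 66,024 / 122,640 = 53.8% (range 0% to 100% by first-dose date)

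**Where in time the loss falls.** If onset is confined to early treatment, the shares are higher:

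| True onset | Day missing | Day and month missing |
|---|---|---|
| Days 1–7 | 86.8% | 98.9% |
| Days 1–28 | 52.3% | 96.0% |
| Days 1–336 | 4.4% | 53.8% |

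Every entry is conditional on the date being partial. None is a share of all AEs.

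**Illustration, hypothetical first dose 18 Sep 2017.**

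| Recorded start | Imputed | TEAE? |
|---|---|---|
| Sep 2017 (true onset 25 Sep) | 1 Sep 2017 | No, lost |
| Oct 2017 | 1 Oct 2017 | Yes |
| 2017 | 1 Jan 2017 | No, lost |
| 2018 | 1 Jan 2018 | Yes |

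**Direction.** The imputed start is never later than the true start. An on-treatment AE can therefore only be moved out of the TEAE count at this boundary, and a true pre-dose AE is never moved in.

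**The case against.** The best case against is that the effect is small and the affected event is not lost from the report. Much of this stands.

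- A reader might infer that on-treatment AEs with partial dates drop out generally. They do not: with only the day missing, an AE in any month after that of first dose stays a TEAE.
- Partial dates should be few. AEs are reviewed at the Day 7 call and at monthly visits (protocol 9.3.2.4 onwards), and SAP 6 requires data queries to be resolved before analysis. A missing month is especially unlikely with contact every four weeks.
- SAP 11.1.1 also presents all AEs by relationship and severity, SAEs, and AEs leading to discontinuation, without limiting these to TEAEs. SAP 7 lists all study data.
- Earliest start with latest end is cautious for event duration. The rule is also the same in every arm.

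A reader might also infer that the rule could hide the drug's hemodynamic or first-dose effects, because the loss concentrates in early treatment. The documents do not support that. Protocol 4.3 places such events mostly in the first hour after dosing. Protocol 9.3.2.3 has the first dose given at the site, with blood pressure and heart rate measured at 30 and 90 minutes and AE monitoring, so these events would normally carry a full date. Where randomization and first dose fall on the same day, the site query covers their timing.

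SAP 7.2 says safety data are analyzed as they were collected, which could be read as no imputation for AEs. That does not close the gap: it leaves no rule for classifying a partial AE date, and the programmer would have to choose one.

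**Conclusion.** The concern holds in a limited form. Followed as written, SAP 7.1 and 11.1.1 misclassify a new on-treatment AE as pre-dose when its day is missing and onset was in the calendar month of first dose, or when day and month are missing and onset was in the calendar year of first dose. A first dose on the 1st, or on 1 January, is the exception. No other rule makes such an AE treatment-emergent.

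On average this covers about 4.4% of treatment days in the first case and about 54% in the second, under the uniform-date assumptions. The effect on any TEAE table cannot be estimated, because the number of partial AE dates is not in the documents, and it is probably small. This is an omission in a safety definition, with a known direction and an easy remedy. It is not evidence that a safety signal would be masked.

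**What to change.** Add to SAP 7.1, with a cross-reference in 11.1.1: if the known parts of a partial AE start date are compatible with onset on or after first dose, impute the later of the first possible day and the first-dose date, and treat the AE as treatment-emergent, unless its stop date (at its latest possible day, if partial) is before first dose. Keep the current rule for medications and medical history. State the TEAE default explicitly, so that an AE imputed to Day 1 does not depend on the same-day site query.

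The share of on-treatment AEs moved before dosing then falls to 0%. The cost is one sentence and a line of code. The downside is that a few AEs from the screening period with partial dates may be counted as TEAEs, which is the conservative direction. Sample size, alpha and the efficacy analyses are unaffected.
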